#### *D. Analysis Plan for Implementation Outcomes*

Process and implementation outcomes will be summarized using descriptive statistics across sites. Further, analyses of the primary outcome (PrEP uptake) and secondary outcomes (persistence/retention on PrEP at 1-month and 4-months within the programme) will be evaluated in conjunction with the implementation outcomes to determine the extent to which process outcomes moderate (effect measure modification) the impact of the intervention.

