Arm 1*	Standard of care	Full-time peer educators employed by the programme to engage women, layer PrEP promotion across prevention programs, and implement “refer a friend” strategies, information, education and communication (IEC) materials, service user testimonials, risk reduction posters to increase young women’s perception of risk, working after hours/weekends to reach young women, working with school governing bodies, and door-to-door outreach.
Arm 2*	Enhanced social media campaign	PrEP social influence campaign, which will use online approaches to promote PrEP within communities in addition to the standard of care activities. Messaging crafted with community input will be geographically targeted to women, parents/mentors, and male partners on Facebook and/or Instagram (final platforms to be determined based on marketing research conducted by Community Health Trust who will contracted to manage the campaign), all with the intention to promote PrEP for women at high risk of HIV infection and change community norms and influence around PrEP. A combination of static imagery and brief videos will be used to engage these groups via social media platforms. High profile social influencers may be engaged as faces of the campaign, including for ads and video creation. A Facebook page will be created and maintained that can be accessed by anyone anywhere, but will only be advertised/promoted in the intervention districts.
Arm 2a**	Nothing additional	Wards in Arm 2a will not receive any additional strategies. They will still receive (as will all arms) the standard of care, as well as the enhanced social media campaign received by all wards in Arm 2.

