**Table 4. Implementation measures to be assessed and the respective data sources**

Implementation Outcomes	Salience	Data Sources and analysis
Acceptability	Satisfaction with social influence campaign components	Cross-sectional survey: descriptive statistics related to acceptability of the social media campaign (captured in post-intervention cross-sectional survey only).
Adoption	Service user uptake and engagement with campaign	Social media metrics: # times each ad was viewed overall and by an individual, # times someone clicked on each ad, and the click-through rate metric which tells you the percentage of people who click an ad out of all the people who saw the ad; we will also assess the number of website/Facebook

		page visits, video views and appointments made.
Costs	Cost-effectiveness and affordability	Costs associated with planning, designing, and implementing the social influence campaign will be assessed
Penetration	Extent to which the social influence campaign reached FSW/AGYW and their families/peers/partners	Cross-sectional survey: descriptive statistics from survey questions on campaign exposure and perceptions among FSW/AGYW and their social support networks
Fidelity	Extent to which the social influence campaign was carried out according to plan	Social media metrics: Social media metrics will be used to assess whether static and video content were shared across platforms as planned; Programme logs: trainings, logs of communication with PrEP champions and community mobilization logs/quality assessments will be assessed to determine the degree to which implementation activities were carried out as planned.

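### Section 7.D treats process outcomes as effect modifiers, but they arise after randomisation and most have no Arm 1 counterpart, so the analysis can only be an observational description within Arm 2

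*Combined protocol and SAP*

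**What the plan says.** Section 7.D opens with a descriptive plan: "Process and implementation outcomes will be summarized using descriptive statistics across sites". It then says that uptake (primary) and persistence at 1 and 4 months (secondary) "will be evaluated in conjunction with the implementation outcomes", and gives the purpose as "to determine the extent to which process outcomes moderate (effect measure modification) the impact of the intervention".

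Table 4 lists five implementation outcomes:

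- **Acceptability:** satisfaction with the campaign, "captured in post-intervention cross-sectional survey only".
- **Adoption:** "Service user uptake and engagement with campaign", taken from ad views, clicks, click-through rate, page visits, video views and appointments.
- **Costs:** "Costs associated with planning, designing, and implementing the social influence campaign will be assessed".
- **Penetration:** "descriptive statistics from survey questions on campaign exposure and perceptions among FSW/AGYW and their social support networks".
- **Fidelity:** whether content was posted as planned, plus training, champion and mobilisation logs.

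Table 1 says the campaign's Facebook page can be opened by anyone but "will only be advertised/promoted in the intervention districts". Champions and mobilisation teams exist only in some Arm 2 wards. Section 7.C gives no model, scale, unit of analysis or handling of Arm 1 for the moderation question.

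**The concern.** Effect modification asks whether the effect of assignment differs across levels of some characteristic. That needs a characteristic with a meaning in both arms, and one that assignment has not itself changed. Process outcomes usually fail on one count or the other: they measure how the intervention was delivered or received.

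At stake is what the trial may conclude from its implementation data. A district where background demand for PrEP is high may both engage more with the advertisements and start more women on PrEP. Under the present wording, that pattern could be read as the campaign having a larger effect where engagement was high. Section 12 plans to share implementation outcomes and uptake results with the funders and the provincial health departments, so the distinction has practical weight.

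**Working it through.** **1. The plan's own figures.** No power or sample size is given for the moderation analysis. The nearest figures, in Section 7.B, are 87% for the main comparison (5 clusters per arm, 5% versus 15%, CV 0.4, 500 to 1000 women per cluster) and 84% for the sub-arms (30 per sub-arm, 10 women each, 10% versus 20%, CV 0.4). Assuming two-sided α = 0.05:

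power = Φ(√[(c − 1)(p1 − p0)² / v] − 1.96), with v = [p0(1 − p0) + p1(1 − p1)]/m + k²(p0² + p1²)

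- Main, m = 1000: v = 0.175/1000 + 0.16 × 0.025 = 0.004175; √(4 × 0.01/0.004175) = 3.095; power 87.2%.
- Main, m = 500: v = 0.00435; √(0.04/0.00435) = 3.032; power 85.8%.
- Sub-arms: v = 0.25/10 + 0.16 × 0.05 = 0.033; √(29 × 0.01/0.033) = 2.964; power 84.2%.

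Both stated figures reproduce. Neither covers moderation.

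**2. Each Table 4 measure against the two requirements.**

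| Measure | Valid value in Arm 1? | Affected by assignment? |
|---|---|---|
| Adoption | No: engagement with the campaign | Yes |
| Costs | No: costs of the campaign | Yes |
| Fidelity | No: delivery of the campaign and its layers | Yes |
| Acceptability | In substance no: satisfaction presupposes exposure | Yes |
| Penetration | Yes: control sites are surveyed | Yes |

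Stray visits to the open page from control districts are possible, but they would not be a valid control counterpart. Appointments, counted under adoption, may also be a step towards starting PrEP, which would make moderation of uptake by that item close to circular.

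**3. Identification.** Write the district-level model as Y = β0 + β1·A + β2·M + β3·A·M, where A is arm and M the process measure. If M is structurally zero in Arm 1, then A·M = M in every district. The last two columns coincide, and a numerical check with 5 + 5 districts gives rank 3 of 4. β2 and β3 cannot be separated. Only the slope of Y on M within Arm 2 is estimable, and assignment does not vary within Arm 2.

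For penetration, M varies in both arms and the model can be fitted. Districts with the same M in different arms are then not comparable groups, because assignment helped to set M.

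**4. How much information remains.** The survey is anonymous with no link-logs (Section 8), and uptake comes from aggregate programme data (Section 5). Survey measures can therefore be joined to programme uptake only by location: 3 districts per arm (Sections 5.C and 7.B). Ad metrics cover at most 5 districts, and no district breakdown is promised. The critical correlation at two-sided 5% is t/√(n − 2 + t²):

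- n = 5: 3.182/√(3 + 3.182²) = 0.878
- n = 3: 12.706/√(1 + 12.706²) = 0.997

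Fidelity logs may offer more points. About 54 wards per sub-arm gives roughly 54 + 54 = 108 wards with champions (2b, 2d) and 108 with mobilisation (2c, 2d).

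**5. Illustration only.** The simulation used 8,000 runs per setting and no true moderation, with Arm 2 uptake 15%, CV 0.4, 1000 women per district, and M correlated ρ with the district's background uptake. The documents give no value for ρ.

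| ρ | Falsely significant, 5 districts | Falsely significant, 3 districts | Median slope, 5 districts (points per SD of M) |
|---|---|---|---|
| 0 | 4.7% | 4.7% | about 0 |
| 0.5 | 11.9% | 6.4% | 2.9 |
| 0.8 | 39.0% | 11.0% | 4.8 |

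This shows a mechanism and its direction. It does not estimate the bias in this trial.

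**The case against.** The best reply is that the impact being moderated need not be Arm 1 versus Arm 2. About 216 wards in the five intervention districts are randomised to 2a to 2d within site, and all of them receive the campaign. Section 7.B states an interest in whether the layers alter the campaign's effect. District-level adoption would be defined in every sub-arm, and its interaction with the within-site sub-arm contrast could be fitted. That is true, but it would rest on five site values and on ad metrics by district, which the documents do not promise. It also leaves the Arm 1 versus Arm 2 reading unidentified.

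Other parts of the reply stand. A reader might infer that the plan prespecifies an invalid interaction test. It does not: Section 7.D names no test or model, and Table 4 speaks of descriptive statistics for acceptability and penetration. A reader might also infer that no moderation quantity could be computed at all. That is too broad, because an interaction with penetration can be fitted; the difficulty there is interpretation. Finally, the plan already handles part of the matter well: Section 4 makes knowledge, attitudes and peer influence secondary outcomes compared across arms, Section 7.B presents the survey as evidence on mechanism, and Section 7.C analyses the responses by difference in differences.

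**Conclusion.** The point holds as a defect in what Section 7.D claims it can determine. For adoption, costs, fidelity and, in substance, acceptability, modification of the Arm 1 versus Arm 2 effect is not identified. For penetration it is computable but would mislead. This follows from the definitions in Table 4 and from where the campaign is delivered, and does not depend on the simulation's assumptions.

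The importance is low. It would be wrong to infer that the trial's main findings are at risk: the primary t-test, its adjusted version, the persistence comparisons and the randomised comparisons among 2a to 2d do not use the process outcomes. It would be equally wrong to quote 39% as this trial's false-positive rate, since that needs an assumed correlation of 0.8, and at zero the rate is 4.7%. The size of any bias cannot be given from the documents.

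**What to change.** Replace the moderation sentence in Section 7.D with text to this effect:

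- Describe uptake and persistence against adoption, acceptability and fidelity within Arm 2 only, labelled observational and non-causal, with the number of districts or wards shown.
- Relate fidelity to ward uptake within site, and only in wards assigned the component concerned: champions in 2b and 2d, mobilisation in 2c and 2d. Neither log has a meaning in 2a.
- Report penetration by arm as an intermediate outcome, beside the knowledge and attitude comparisons already planned.
- Reserve the term effect modification for baseline factors, such as programme type (already used to constrain the randomisation), and for the randomised layers 2a to 2d.

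The cost is a change of wording; no new data or sample is needed. The ward-level description depends on logs that can be assigned to wards. The downside is that the claim about moderation by process outcomes is given up.

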**Table 4. Implementation measures to be assessed and the respective data sources**

Implementation Outcomes	Salience	Data Sources and analysis
Acceptability	Satisfaction with social influence campaign components	Cross-sectional survey: descriptive statistics related to acceptability of the social media campaign (captured in post-intervention cross-sectional survey only).
Adoption	Service user uptake and engagement with campaign	Social media metrics: # times each ad was viewed overall and by an individual, # times someone clicked on each ad, and the click-through rate metric which tells you the percentage of people who click an ad out of all the people who saw the ad; we will also assess the number of website/Facebook

		page visits, video views and appointments made.
Costs	Cost-effectiveness and affordability	Costs associated with planning, designing, and implementing the social influence campaign will be assessed
Penetration	Extent to which the social influence campaign reached FSW/AGYW and their families/peers/partners	Cross-sectional survey: descriptive statistics from survey questions on campaign exposure and perceptions among FSW/AGYW and their social support networks
Fidelity	Extent to which the social influence campaign was carried out according to plan	Social media metrics: Social media metrics will be used to assess whether static and video content were shared across platforms as planned; Programme logs: trainings, logs of communication with PrEP champions and community mobilization logs/quality assessments will be assessed to determine the degree to which implementation activities were carried out as planned.

## **8. ACCESS TO SOURCE DATA / DOCUMENTS:**

Study documentation, including but not limited to the research plan, consent form, study tools, standard operating procedures, etc., will be securely shared between the coordinating centre and all partners by means of a preset Dropbox Business folder specifically developed for this study. Access to the Dropbox folder will be by email invitation only. As study documents are changed, official amendment requests will be put through to both the JHU IRB and the IRB at the University of Pretoria.

Source data will be collected, managed and protected using REDCap, a secure, encrypted online platform, and in accordance with a detailed Standard Operating Procedure (SOP) for Data Management. All computers with data will be protected by passwords, data files will be stored in encrypted folders on Johns Hopkins OneDrive, and hard copies of data kept in a secure cabinet or room with limited access by individuals on the study team. All consent forms will be stored separately from other study documents, in a discrete secure cabinet or room. Data from the cross-sectional survey will be anonymous, so no generation of link-logs or other databases with identifying information will be created. All programme data available to JHU or collaborators outside of TB HIV Care will be de-identified. For the cross-sectional survey, tablets and computers will be password protected, returned to the office on a daily basis, synced and stored in a locked cabinet. Hard paper copies will be available as back-ups in the event that the electronic systems are not working and then entered within two business days into the electronic data collection system. Paper copies will be returned to the office on a nightly basis by a designated study staff, trained in data security, and stored securely in a locked cabinet. Paper-based and electronic data will be kept for no longer than

10 years following study completion. Specifically, informed consents will be destroyed 10 years following completion of the study.

## **9. QUALITY CONTROL AND QUALITY ASSURANCE:**

Data quality control and quality assurance is imperative to ensuring that all research results are of high quality and are valid. Moreover, systematic and continuous quality control measures and a detailed quality assurance plan is central to making sure that research activities are conducted as planned and to avoid poor data results, wasted time, effort, and resources. Therefore, the study has enacted a number of quality assurance and control measures.

Furthermore, all study staff will undergo good clinical practice training, focusing on data quality control and quality assurance, and follow daily quality control measures put forth within the protocol, data monitoring plan, and directly by the programme coordinator and investigative team. All study staff will be held accountable for data quality.

Inbuilt measures will help support and ensure quality assurance. Data will be collected, managed and protected using REDCap. Tablets will be disinfected before and after use to prevent possible transmission of Covid-19. The questionnaires will be programmed with built in skip patterns and validation rules. Validation rules (e.g. valid data ranges or logic checks) assist in ensuring that data is captured and recorded in a standardized way. The questions will also be programmed to ensure no question is left blank and/or skipped by ensuring that the data collector indicates some sort of refusal or 'do not know' options to the unanswered question. Electronic data collection will allow for real-time data monitoring and review to ensure that quality assurance and quality control measures are effectively being implemented and possible issues are being appropriately addressed. Paper-based and electronic data will be kept for no longer than 10 years following study completion.

Ongoing internal monitoring will be conducted on a daily basis, led by the study coordinator based in Pietermaritzburg, and presented to the investigative team on a weekly basis. The internal monitoring will ensure quality control by actively identifying and mitigating issues, ensuring proper informed consent documents are in place, eligibility criteria preserved, and data quality. Additionally, a source documentation checklist will be employed to ensure all study related activities are carried out as stipulated in the protocol and in a consistent way.

Development of a structured procedures manual will also act as a data quality control strategy. Study procedures will be presented in an instruction-based format and anticipated unexpected circumstances and potential solutions are presented. Moreover, there will be a specific SOP in place to guide and ensure quality control systems. The team will run daily and weekly quality control reports that will identify and flag potential issues.

## **10. PROTECTION OF HUMAN SUBJECTS:**

This study will take preemptive and ongoing measures to ensure the protection of human subjects before, during and after the research study. The study team will ensure participants' privacy is safeguarded and the confidentiality of their data are protected. Moreover, through the process of informed consent, all individuals participating in the study will be participating voluntarily and with full knowledge of the study procedures, duration, risks, and benefits.

### *A. Declaration of Helsinki*

The ethical principles outlined with the Declaration of Helsinki guide this research. The wellbeing of the participants takes upmost importance and precedence over the proposed research and interest of

science and society. This research is held to ethical standards that promote respect for persons and protect their health and human rights. Moreover, given that this research involves vulnerable populations, specific and special attention has been inbuilt to ensure the protection of these individuals. As a result, the study has been reviewed and will be approved prior to launch by the ethical review boards at Johns Hopkins Bloomberg School of Public Health and University of Pretoria. Participation in the study is voluntary and all subjects must provide informed consent to enroll.

*B. Institutional Review Board*

The clinical site will use the Faculty of Health Sciences Research Ethics Committee of the University of Pretoria for this study. Approval will also be ascertained by the JHU IRB, which will collect IRB approvals and renewals from the University of Pretoria.

Johns Hopkins Bloomberg School of Public Health

**The Faculty of Health Sciences Research Ethics Committee**

FWA: FWA00002567

Address: [name]

[name], [name]

[name]

[name]

[contact]

*C. Potential Risk*

There are no direct physical risks related to this research. The service user participants could be harmed if individuals outside of the study found out about their participation in the study and discovered that they are at risk for acquiring HIV, though given that they will be encountered only during clinical interactions or at FSW/AGYW community sites, we believe this risk to be very low. Other risks include negative impact on social standing with peers and family, loss of relationship with partner, arrest/incarceration/fine (if female sex workers), or discrimination from medical personnel, friends or family members if confidentiality is breached. However, due to strict confidentiality procedures, we do not anticipate disclosure of HIV risk, unless revealed by the participant.

**Social influence campaign:** As the campaign activities will not be targeted at any specific individuals but rather throughout specific cities, we anticipate limited risks associated with these activities. The campaign activities are meant to promote sexual health and well-being, however it is possible that individuals may interact with the social media campaign (e.g. post publicly onto Facebook) and share details or information that may cause them harm or harm others; we anticipate this risk to be low as we anticipate most of our target population has some experience using social media platforms; we will monitor and delete posts that are

harmful to others (e.g. bullying) and diligently foster a positive social media environment that limits misinformation or malignment.

**Cross-sectional surveys:** It will be made clear that there are no negative consequences to HIV prevention services for TB HIV Care programme users who choose not to participate in the survey and that data collection will be anonymous; the age of the young woman and the location will be recorded, however only limited information related to her sexual and health-seeking behavior or health will be captured and she will remain anonymous. We will request to use written consent for these brief cross-sectional surveys and participants will indicate their consent to participate by signing the consent form; participants that cannot write or who have privacy concerns may request to sign with an 'X', for which a witness will need to be present and sign in addition to the researcher. . Potential participants will be approached discretely and surveys will be conducted in a private and secure location in order to ensure privacy.

**Assessment of PrEP programme data:** Since no individual human subjects will actually be recruited, we do not anticipate that there will be any risk to the individual. Data on PrEP initiations and follow-up visits will be assessed at the aggregate level within the program, and no personally identifiable information will be collected for this activity.

**Social media metrics:** Since no individual human subjects will actually be recruited, we do not anticipate that there will be any risk to the individual. Social media metrics are reported at an aggregate level and only deidentified publicly visible quotes will be used, and therefore no PII information will be collected for this activity.

To minimize the risk that confidentiality is breached, no names will be stored except for signed consent forms which will be kept separate from all study data in a secure and locked cabinet. In addition to all data being reported anonymously, we will ensure that any contextual information that might identify a particular individual will not be reported in publications or reports that result from this study. Participants will be offered a copy of the consent form but will not be required to take it. All participation will be voluntary, and declining participation will not affect access to existing health services available through TB HIV Care.

Additionally psychological and psychosocial referrals will be provided to participants as needed. This research will operate embedded within the existing TB HIV Care program. Therefore, psychological and psychosocial referral systems within the study will be based on existing referral systems within the TB HIV Care program.

